SUMMARY

Rationale: Infertility is a worldwide problem and about 10%-15% of all couples will be affected by the inability to have children. In approximately 50% of infertile couples a male factor is involved. In the past decade, the role of oxidative stress on sperm has been researched thoroughly and found to be the problem in 30% to 80% of male infertility cases. Impryl® is a nutritional supplement which works on the metabolic system and regulation of oxidative stress by activating the 1-Carbon cycle and therefore recycling of homocysteine.

Objective: To determine the effectiveness of nutritional supplement Impryl® in men of infertile couples on ongoing pregnancy rate, with or without assisted reproduction technology (ART).

Study design: Multicentre, randomised double blind placebo controlled clinical trial/superiority study.

Study population: All participants in this study are male adults, age 18-50 years, part of a couple that is diagnosed with infertility, regardless the outcome of semen analysis. The couple will either start or is already started with fertility treatment, i.e. expectative management (EM, duration 6 months), intra-uterine insemination (IUI) with or without ovarian stimulation (mild ovarian hyperstimulation (MOH) or ovulation induction (OI)), either in vitro fertilization (IVF) or intracytoplasmic sperm injection (ICSI) treatment.

Intervention: Impryl® or placebo, with identical appearance one tablet each day for a total duration of maximal 6 months. Patients can start directly with fertility treatment and/or to conceive.

Main study parameters/endpoints: The primary outcome is the number of ongoing pregnancies confirmed by ultrasound at ≥ 10 -12 weeks, and conceived in the time window between randomization up to and including month 6 of intervention use. Secondary outcomes are change in semen parameters between baseline and 3 months intervention in IUI/IVF/ICSI group, based on (pre-wash) total motile sperm count (TMSC), leading to a different fertility treatment categorisation. Furthermore the number of pregnancies conceived in the optimal intervention time window, the overall number of pregnancies, time to pregnancy, embryo fertilization rate in IVF/ICSI, embryo-utilization rate in IVF/ICSI, number of miscarriages and live birth rate are documented within the study period of 15 months. The occurrence of adverse events will be reported.

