1.3 Sample size calculation

The overall success rate (number of ongoing pregnancies, not specified per cycle number) in IVF and ICSI in the Netherlands was respectively 19.8% and 21.5% per cycle in 2015.(23) The cumulative number of ongoing pregnancies in IUI is estimated to be around 5 to 13% per cycle, around 18% after three cycles and 20-30% after six cycles. (24-26) Based on our Radboudumc data, the ongoing pregnancy rate in EM is estimated around 20% after 6 months.

A Cochrane review ‘antioxidants for male subfertility’ estimated the increase in clinical pregnancy rates after use of antioxidants with an Odds Ratio (OR) of 3.43 (95% CI 1.92 to 6.11, $P < 0.0001$, 7 RCTs, 522 men, $I^2 = 0\%$, low quality evidence). (27) However, this concerns low quality evidence, and the included population in this Cochrane review was couples with male factor subfertility, whereas in our study we also include couples with unexplained infertility. Therefore, we assumed a more conservative OR of 1.5. Assuming a 20% ongoing pregnancy rate in the placebo group, this reflects in an expected pregnancy rate of 27.3% in the Impryl® group

The study is designed as a superiority study. Based on the above mentioned data, we expect a 7.3% increase in ongoing pregnancy number when men are treated with Impryl® compared to placebo. However, after randomization patients can directly start with both intervention and achieving a pregnancy, either spontaneously or with fertility treatment. In these first months the effect of the intervention is expected to be suboptimal due to the duration of the spermatogenesis (72 days before whole renewal). Therefore we adjusted the expected increase of 7.3% to a more realistic effect of 6.5%. We assume an equal increase in all fertility groups (meaning EM, IUI and IVF/ICSI) from 20% to 26.5%.

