The ratio between the 3 fertility treatment groups (EM 1: IUI 3: IVF/ICSI 2) is based on the number of new patients treated at Radboudumc and the sites each year. To test the effect of Impryl on the probability of ongoing pregnancy, a sample size of 600 men per treatment group (1200 in total) is needed, assuming differences in ongoing pregnancy rates of 6.5% and an expected ongoing pregnancy rate of 20% in the placebo group, with a two-sided alpha of 5% and a beta of 24% (i.e. 76% power). As we expect the number of participants lost to follow up to be minimal. We will allocate 600 patients in both intervention and control arm. Figure 1 shows the distribution of the number of participants for the 3 different types of fertility treatment (EM, IUI and IVF/ICSI).

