Semen analysis will be performed two times: once during diagnostic work-up (standard care, analysis according to WHO criteria(28) and once more after approximately 3 months of using study medication (ie. after three months of IUI treatment or IVF/ICSI). At several sites, a pre-wash TMSC is standard care when performing an insemination (IUI group) and will be performed on the semen produced for IVF/ICSI as part of routine measurement before procedure. Because semen analysis performed at the time of treatment cannot be fully performed according to the WHO criteria, we will categorize the TMSC quality according to the allocated treatment category. This means, that the TMSC (evaluated at the start of treatment and after 3 months) will be analyzed according to changes in allocated treatment category based on the NVOG guideline(29). The criteria for treatment are given in the table below. A change in treatment category means an improvement in sperm quality that would allow a lower treatment category (e.g, from ICSI to IVF)

| TMSC outcome ($\times 10^6$) | WHO Diagnostic category | NVOG Treatment category |
|--------------------------------|-------------------------|---|
| > 10 | Normospermia | EM |
| 3 -10 | Mild OAT | IUI |
| 1-3 | OAT | IVF/ICSI (if after wash VCM is <0,5) |
| <1 | Extreme OAT/Azoospermia | ICSI |

OAT = oligo-astheno-teratozoospermia.

* Or IVF depending on the prediction model of Hunault and other clinical characteristics

We decided not to perform a semen analysis in the EM group due to the fact that they already have normal semen parameters at intake and the burden of an extra visit is high.

Fertilization and embryo-utilization rate

In IVF/ICSI patients fertilization rate and embryo-utilization rate are standard reported by every IVF-laboratory. Fertilization rate is the percentage of oocytes with ≥ 2 PN after insemination (IVF) or injection (ICSI). The embryo-utilization rate (EUR) is defined as the number of high quality embryos obtained, embryo's used at transfer plus the number of embryos frozen, divided by the number of zygotes obtained in a cycle. Due to the differences in embryo evaluation and embryo selection criteria for cryopreservation, we decided to measure the relative increase in fertilization and utilization rate observed for each clinic.

Transvaginal ultrasonography

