7. STATISTICAL ANALYSIS

All data will be analyzed on an intention-to-treat basis. Data of patients who are lost to follow-up, will be included in their randomised group

will be included in their randomized group:

- Patients who are lost to follow-up during the treatment period are considered not to have achieved a pregnancy.
- Patients, who are lost to follow-up right after achieving a pregnancy of less than 8 weeks of gestation, are considered not to have achieved an ongoing pregnancy
- Patients, who are lost to follow-up right after achieving a pregnancy of 8 or more weeks of gestation, are considered to have achieved an ongoing pregnancy.

In addition, a per-protocol analysis will be performed for the primary outcome and the secondary outcomes overall pregnancy number, time to pregnancy, number of miscarriages and live birth rate.

Descriptive statistics will be calculated to check for major dissimilarities between study groups with respect to baseline information. Baseline data will be described quantitatively. For continuous variables, we will examine the distribution of the observations, and if normally distributed we will summarise them as means with standard deviations (SDs). If they are not normally distributed, then medians and inter-quartile ranges (IQRs) will be reported. For dichotomous data, we will provide counts and proportions.

The primary outcome variable 'ongoing pregnancy' will be assessed as follows. The ongoing pregnancy percentages as observed in the trial will be presented for both treatment arms, overall, and separately for the three strata (i.e. EM, IUI, IVF/ICSI). In order to adjust for possible imbalances between the treatment groups, the pregnancy percentages and differences in pregnancy percentages between the experimental and control group, and the corresponding 95% confidence intervals will be estimated using a fixed effects binomial model with an identity link, including intervention, fertility treatment, centre and female age (centered). If this model does not converge, a logit link will be used.

Time to ongoing pregnancy will be evaluated by the Kaplan-Meier approach; differences between the two arms will be tested with the log-rank test. Similar analyses will be conducted per stratum (EM, IUI or IVF/ICSI). The other secondary outcomes (overall pregnancy number, number of miscarriages, live birth rate, fertilization rate, embryo-utilization rate) will be evaluated similarly to the primary outcome. Changes in semen

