analysis, leading to different fertility treatment categorisation, will be first calculated with descriptive statistics, with the following codes:

- 0: if there is no change in treatment category
- 1: if there is 1 category change (i.e. from IUI to EM), or -1 if it goes from less severe to severe (i.e. IUI to IVF)
- 2: if there are 2 category changes (i.e. from IVF to EM)

The changes will be summarized with descriptive statistics (mean, SD, median, range) and frequency tables per treatment and stratum. Further, the difference between the experimental and control group will be assessed with a fixed effects linear model, adjusted for centre and stratum.

Furthermore, adverse events will be summarized. Sensitivity analyses will be performed to evaluate possible effects in case of protocol amendments.

The per-protocol population will consist of all randomised patients without any major deviation from the protocol. A major protocol deviation is defined as

- Use of other nutritional supplements without a wash-out period
- Intake of study medication of less than 75% of the prescribed amount

Participants will be asked by automatic email to report in Castor their actual compliance to the intervention by taking note of total amount of consumed study medication (used boxes and tablets). Patients will also be asked to report about major changes of their lifestyle occurring during the study period (see page 22).

The results will be extracted from Castor. If there are missing data this will be mentioned along with the reason.

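### The model for change in semen treatment category omits the baseline TMSC category, which is already collected and, with TMSC bands as the start, bounds the score

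*Combined protocol and SAP*

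**What the plan says.** Section 7 scores each man by the number of treatment categories he moves between baseline and about 3 months. The printed codes are 0, 1, -1 and 2, the last being "2: if there are 2 category changes (i.e. from IVF to EM". For the comparison of arms, "the difference between the experimental and control group will be assessed with a fixed effects linear model, adjusted for centre and stratum". No other section adds baseline TMSC or its category.

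Section 5.3 supplies the data: "Semen analysis will be performed two times: once during diagnostic work-up", and again after about 3 months of study product. Its table maps TMSC (million) to treatment: above 10 is EM, 3 to 10 is IUI, 1 to 3 is IVF/ICSI, below 1 is ICSI. The EM group has no second measurement: "We decided not to perform a semen analysis in the EM group".

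On who is measured, the Summary admits men "regardless the outcome of semen analysis", and section 1.3 contrasts the trial with a review of male-factor couples, "whereas in our study we also include couples with unexplained infertility". The primary model in section 7 goes beyond the randomisation factors, "including intervention, fertility treatment, centre and female age (centered").

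**The concern.** A change score on a closed scale depends strongly on where a man starts. If that start is not in the model, its variation stays in the residual and widens the confidence interval. Any chance difference between arms in baseline category also goes uncorrected. These are two views of one cost, not two harms. Because allocation is randomised within stratum and centre, the estimate stays unbiased.

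What is at stake is the precision of one secondary outcome in a subset whose size is not stated. The plan already shows the relevant thinking by putting female age into the primary model; the starting value of a change score is an even more direct candidate.

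**Working it through.** **Plan's own figure.** No power is given for the semen outcome. The only power figure is 76% for ongoing pregnancy (section 1.3). With n = 600 per arm, p1 = 0.20, p2 = 0.265 and mean p = 0.2325:

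power = Φ[(√600 × 0.065 − 1.96 × √(2 × 0.2325 × 0.7675)) / √(0.20 × 0.80 + 0.265 × 0.735)] = Φ[(1.592 − 1.171) / 0.596] = 0.760.

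It reproduces, and it does not bear on this point.

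**Step 1: how the start bounds the score.** Number the levels ICSI 0, IVF 1, IUI 2, EM 3. With baseline b, the change lies between −b and 3 − b.

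| Baseline band (million) | Lowest score | Highest score |
|---|---|---|
| <1 | 0 | +3 |
| 1–3 | −1 | +2 |
| 3–10 | −2 | +1 |
| >10 | −3 | 0 |

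**Step 2: does stratum carry the same information?** Without EM men, stratum has two levels here, and one of them merges IVF with ICSI. Stratum is the fertility treatment, and section 1.2 sets no semen threshold, so bands can vary within each level.

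**Step 3: precision lost, with TMSC bands as the start.** Section 1.3 gives "The ratio between the 3 fertility treatment groups (EM 1: IUI 3: IVF/ICSI 2"), so of 1,200 men, 1,200 × 3/6 = 600 are IUI and 1,200 × 2/6 = 400 are IVF/ICSI. The ceiling is 1,000; fewer will have a pre-wash TMSC. The rest is assumed, not in the documents:
- log-normal TMSC, cut at 1, 3 and 10;
- medians (IUI, IVF/ICSI) of (10, 3), (20, 10) or (10, 1.5);
- log SD 1.0 or 1.5;
- within-stratum correlation between the two measurements from 0.3 to 0.9.

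With 300,000 simulated men per setting, ratio = residual variance with stratum and baseline band ÷ residual variance with stratum only.

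| Correlation | Variance left |
|---|---|
| 0.3 | 0.61–0.63 |
| 0.5 | 0.69–0.72 |
| 0.7 | 0.78–0.81 |
| 0.9 | 0.88–0.91 |

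Overall range 0.608 to 0.912. Standard error ratio: √0.608 = 0.78 to √0.912 = 0.95. Equivalent sample: 1/0.912 = 1.10 to 1/0.608 = 1.65. In these settings 31 to 65% of men start in the top band.

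**Step 4: chance imbalance.** The slope of change on baseline band, given stratum, is 0.18 to 0.78 in size (negative in sign). A difference of 0.1 category between arms at baseline shifts the planned estimate by 0.1 × 0.18 = 0.02 to 0.1 × 0.78 = 0.08.

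**Step 5: with centre in the model.** Simulated trials (1,500 per setting) used the 17 listed centres, n = 300 or 1,000, an assumed centre SD of 0.3 and an assumed arm shift of 0.2, both on the log scale, with medians (10, 3) and (20, 10) and log SD 1.0. The two models gave the same mean difference within 0.003, and the empirical variance ratio was 0.57 to 0.89. Example: n = 1,000, medians (10, 3), correlation 0.5: SE 0.052 without and 0.044 with the baseline band.

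**Step 6: other assumptions.** With medians 8/2, 15/5 or 30/10, between-man log SD 1.2, within-man log SD 0.6 or 0.9, arm shift 0.2 and 500 or 1,000 men, variance falls by 15 to 27% and the SE by 8 to 15%. With 500 men, medians 15/5 and within-man SD 0.6, the estimate is 0.107 in both models, the SE goes from 0.058 to 0.053 and power from 45% to 52%.

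**Step 7: if the score starts from the allocated treatment instead.** In the Step 3 settings, the variance left is 0.36 to 0.95 with IVF and ICSI merged, and 0.40 to 0.96 with four levels (assuming ICSI means baseline TMSC below 1 in the IVF/ICSI stratum), with the band entered as categories. Entered as one linear term, the overall range is about 0.38 to 1.00.

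**Step 8: printed codes.** Against 0, 1, −1 and 2, transitions without a code number 4 of 16 with a TMSC-band start (−3 once, −2 twice, +3 once), 2 of 12 with an allocated start (−2, +3), and 0 of 6 with an allocated start and IVF/ICSI merged. With a band start, 0 to 12.5% of simulated men fall in these cells.

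**The case against.** The strongest objection is that the start may be the allocated treatment, since section 5.3 also speaks of allocated treatment category. With IVF and ICSI merged, stratum then is the starting category and is already in the model, and this is the one reading under which the printed codes are complete. However, section 5.3 describes TMSC assessed both when treatment starts and 3 months later, the secondary objectives define the change from baseline on TMSC, and section 5.1.2 lists four categories. Even under the allocated reading, the baseline band as a prognostic covariate still gains precision in nearly all settings (Step 7).

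Three smaller points stand in part:
- Section 5.3 names both the work-up and the start of treatment, so the baseline sample must be fixed before the covariate can be used. TMSC is also absent from the baseline list in section 5.1.3.
- The size of the gain rests entirely on assumed distributions.
- Female age is not a baseline value of the outcome, so the primary model illustrates the principle but sets no rule that the semen model breaks.

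The planned check of baseline dissimilarities and the frequency tables by treatment and stratum would display an imbalance but not adjust for it.

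**Conclusion.** The concern holds. The planned analysis is valid and unbiased but less precise than the collected data allow. With TMSC bands as the start, the illustrative gain from adding the baseline band is 9 to 39% of residual variance, equal to the precision of about 10 to 65% more men. The direction is the same under every band-start assumption tried; only the size depends on the assumed medians, spread and correlation. The statement that baseline bounds the score applies to the band reading, which the text favours but does not fix. The incomplete code list is a matter for clarification, since the missing values follow from the sign rule in section 7. The weight is limited to one secondary outcome in a subpopulation.

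**What to change.** Add the baseline TMSC category, entered as categories, to the linear model alongside centre and stratum.

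Before unblinding, and for scoring only:
1. Name one baseline sample and one mapping from TMSC to category for both time points, including how the 1 to 3 million band, which the table labels IVF/ICSI with a post-wash condition, is scored.
2. Score the signed number of categories moved over the full range, up to −3 to +3 with four levels.
3. Reconcile section 5.3, where a change is described as an improvement, with section 7, where it may also be a worsening, and settle whether IVF and ICSI are separate levels (sections 5.1.2, 5.3 and 7).

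The cost is SAP wording. No visit or sample is added: the baseline analysis is part of the work-up, and a band-based score cannot be computed without it. The sponsor should confirm that the chosen baseline value is held in the trial database.

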7.1 Interim analysis

Given the low risk on adverse events of a nutritional supplement, there are no planned interim analyses.

8. ETHICAL CONSIDERATIONS

8.1 Regulation statement

The study will be conducted according to the principles of the Declaration of Helsinki as amended most recently by the 64th WMA General Assembly, Fortaleza, Brazil, October 2013 and in accordance with the Medical Research Involving Human Subjects Act (WMO).

8.2 Recruitment and consent

Potential subjects will be informed by the treating physician about the study. All subjects will be handed an PIF at their intake consultation. The information letter also contains contact information of the coordinating investigator. If requested the (potential) subject could also receive additional information from the coordinating investigator ([name]) or they will get a telephonic consultation with an onsite research nurse. Only after counselling and reading the additional information the (potential) subject will be asked for their informed consent. A consent form must be signed by both the couple as the physician or research nurse who provided the information. Couples will receive the information preferably at or before (together with appointment letter) their first consultation. The following consultation the subject will be asked whether he will or will not participate. If a patient needs more time or only has one evaluation consult in between IVF/ICSI treatment, they will be telephonically contacted by the onsite research nurse or research coordinator to ask for participation. The information letter and informed consent are attached.

8.3 Objection by minors or incapacitated subjects

Not applicable.

8.4 Benefits and risks assessment, group relatedness

As this study compares a food supplement with placebo, it will not impose extra risk on participants. Infertility is a common problem which affects many couples. Therefore research in order to optimize treatment is imperative.

8.5 Compensation for injury

The sponsor/investigator has a liability insurance which is in accordance with article 7 of the WMO. The sponsor (also) has an insurance which is in accordance with the legal requirements in the Netherlands (Article 7 WMO). This insurance provides cover for damage to research subjects through injury or death caused by the study.

The insurance applies to the damage that becomes apparent during the study or within 4 years after the end of the study.

8.6 Incentives

Subject will receive no special incentives or compensation.

9. ADMINISTRATIVE ASPECTS, MONITORING AND PUBLICATION

9.1 Handling and storage of data and documents

Data will be collected in an online registration system (Castor) by the coordinating investigator or research nurses. Data handling will be done anonymously, with the patient code only available to the local investigator and the research nurse working in the local centre. The data will be preserved for the duration of 15 years. The handling of personal data complies with the Dutch Personal Data Protection Act (in Dutch: De Wet Bescherming Persoonsgegevens, WBP).

9.2 Monitoring and Quality Assurance

Monitoring will be performed in compliance with Good Clinical Practice (GCP) and other rules and regulations in order to achieve high quality research and secure patient safety.

9.3 Amendments

A 'substantial amendment' is defined as an amendment to the terms of the METC application, or to the protocol or any other supporting documentation, that is likely to affect to a significant degree:

- the safety or physical or mental integrity of the subjects of the trial;
- the scientific value of the trial;
- the conduct or management of the trial; or
- the quality or safety of any intervention used in the trial.

All substantial amendments will be notified to the METC and to the competent authority. Non-substantial amendments will not be notified to the accredited METC and the competent authority, but will be recorded and filed by the sponsor.

